13. MEDICAL HISTORY

Medical History information including the concomitant illness (Ongoing at Study Entry, or start on or after the Study Entry) for this study is not complete entry for most subjects and is collected only for a small portion of the subjects whose information is collected from the eCR. This information will be presented in a set of summary tables and listing. Medical History for other subjects whose information are not collected in this study will be integrated from their feeder study (AT1001-041 and AT1001-012) as Medical History, and this information will not be included in SDTM or ADaM dataset, and will only be presented in a separate set of summary table and listing. All Medical History will be coded using version 16.1 of MedDRA and presented by SOC and PT for the ITT population.

14. MEDICATIONS

Medications will be coded using September 2013 version of the World Health Organization Drug Dictionary Enhanced (WHO-DDE) and presented for the ITT population, and a table will be provided to summarize the medications by ATC Level 3 and PT. Medications will similarly be summarized for subjects taking ACEi/ARB/RI. A listing of all medications will be provided for ATC Level 3 and PT. In addition, a listing presenting the enzyme replacement therapy (ERT) history will be provided.

15. STUDY MEDICATION EXPOSURE AND ACCOUNTABILITY

Migalastat HCl, 150 mg per capsule, and reminder capsules in blister packs will be administered at the baseline visit and subsequent visits in 6-month intervals. Subjects are expected to take one 150 mg capsule every other day (QOD)

Document: \\quintiles.net\enterprise\Sites\CAMTL\IntProjects\SasData\Amicus\AT1001\AXA23225A\Biostatistics\Documentation\SAP\DR\Amicus_AT1001-042_SAP_Final_v1.0_20190821.docx

Author: Amicus

Version Number: Final v1.0

Version Date: 21AUG2019

Template No.: CS_TP_BS016 Revision 5

Reference: CS_WI_BS005

Effective Date: 01Apr2018

except for the Addendum 1.1.2 subjects, who are expected to take one 150 mg capsule on every 4th (Q4D) or 7th day (Q7D)..

Exposure to study medication will be presented for the ITT population by descriptive statistics. The date of first and last study medication administration will be taken from the eCRF Study Drug Administration form for duration of exposure as follows, and interruptions, compliance, and dose changes are not taken into account for duration of exposure.

Duration of exposure (days) = date of last study medication administration – date of first study medication administration + 1.

Duration of exposure (months) = Duration of exposure (days) / (365.25/12) rounded to one decimal place.

Duration of exposure [months] categorized by 6-month interval up to 48 months will also be included in the table. Listings presenting the study drug administration information including duration of exposure and drug accountability will be provided. In addition, a listing is provided to present dosing regimen for Addendum 1.1.2.

16. STUDY MEDICATION COMPLIANCE

Compliance to study medication will be presented for the ITT population. Since no patient diary will be filled for ITT population and only a study drug administration eCRF page will be completed to capture the first and last dose date, an estimate of the compliance will be calculated as follows:

$$\text{Compliance} = \frac{[(\text{Last dose date} - \text{first dose date}) + 1]/2 - \text{missed doses} + \text{extra doses}}{[(\text{Last dose date} - \text{first dose date}) + 1]/2} \times 100\%$$

Descriptive statistics for the compliance (n, mean, median, standard deviation, minimum, maximum values) will be presented and a frequency distribution will be computed for the following categories: < 80%, >= 80 - <120%, and >= 120%.

A listing presenting the overall study medication compliance will be provided.

17. EFFICACY OUTCOMES

17.1. EFFICACY OUTCOMES AND VARIABLES

All efficacy outcomes will include all subjects (excluding the renal impairment subject) and will be summarized using nominal visits (not including unscheduled visit or early termination) and descriptive statistics. Efficacy assessments will be performed at the Baseline Visit, followed by subsequent clinic visits in every 6 months until the

Document: \\quintiles.net\enterprise\Sites\CAMTL\IntProjects\SasData\Amicus\AT1001\AXA23225A\Biostatistics\Documentation\SAP\DR\Amicus_AT1001-042_SAP_Final_v1.0_20190821.docx

Author: **Amicus** Version Number: **Final v1.0**
 Version Date: **21AUG2019**

Template No.: CS_TP_BS016 Revision 5 Reference: CS_WI_BS005

Effective Date: 01Apr2018

End of Study visit. All efficacy outcomes will follow the same visit pattern unless otherwise specified. Descriptive statistics will be calculated for baseline and each post-baseline visit (as well as time point if applicable), followed by change from baseline at that visit. Baseline is defined in section 7.2, whereas change from baseline is defined in section 7.6.

The efficacy endpoints to be presented are

- eGFR_{MDRD} and eGFR_{CKD-EPI}
- Plasma lyso-Gb₃ (Plasma globotriaosylsphingosine)
- Measurement of white blood cell (WBC) α-Gal A activity
- Measurement of 24-hour urine protein
- Measurement of left ventricular mass (LVM) and LVM index (LVMi), as assessed by echocardiography
- Measurement in ejection fraction, as assessed by echocardiography
- Measurement of fractional shortening, as assessed by echocardiography
- Measurement of left ventricular internal dimension (LVIDd and LVIDs), midwall fractional shortening (MWFS), and wall thicknesses, as assessed by echocardiography
- Measurement of patient reported Quality of Life as assessed by the Short Form 36 (SF-36)

Each endpoint (consisting of one or more variables) will be summarized in a table. Listings will be provided by domain or sub-domain categories, e.g. Laboratory categories - Chemistry, Hematology, Urinalysis, Echocardiography, and Questionnaire.

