Since Fabry disease is a chronic condition, typically resulting in declining renal function, and usually requiring life-time treatment, the current study (AT1001-042) was designed to provide continued migalastat HCl treatment to those subjects who have completed treatment in a previous migalastat study, as well as to enable collection of longer term safety and efficacy data. However, previous Phase 1 studies with migalastat HCl have shown migalastat HCl to be primarily excreted (77% of the dose) via the kidneys. Therefore, it is not unexpected that migalastat HCl would demonstrate increased systemic exposure with declining renal function. A Phase 1 renal impairment study, AT1001-015, conducted in non-Fabry patients with varying stages of renal impairment and normal renal function demonstrated significant accumulation of plasma migalastat in subjects with $eGFR < 30 \text{ mL/min/1.73m}^2$.

Eleven subjects had > 2-fold increase in AUC relative to the mean (12400 ng·hr/mL) of normal renal function ($> 90 \text{ mL/min/1.73m}^2$) in study AT1001-015. Eight of the 11 subjects had severe renal impairment ($< 30 \text{ mL/min/1.73m}^2$) with 2.9- to 6.7-fold increased area under the concentration-time curve (AUC), and all 8 had elevated ($> 100 \text{ ng/mL}$) trough concentrations of plasma migalastat from 238 to 582 ng/mL. Based on AT1001-015 results, an $eGFR$ of $< 30 \text{ mL/min/1.73 m}^2$ in non-Fabry subjects is associated with plasma migalastat accumulation.

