6.4. Withdrawal Criteria

Subjects may discontinue migalastat HCl and withdraw from the study for any reason including, but not limited to, the following:

- At their own request or at the request of their parent or guardian (if the subject is a minor) or legally authorized representative*.
- If, in the investigator's opinion, continuation in the study would be detrimental to the subject's well-being.
- Occurrence of an intolerable adverse event (AE) as determined by the investigator and/or the subject.
- Subject initiates or plans to initiate regular ERT for Fabry disease.
- Suspected hepatotoxicity, as defined by increase of ALT or AST $\geq 3X$ upper limit of normal (ULN) and total bilirubin $> 2X$ ULN when no other reason can be found to explain the increase in liver enzymes.
- Persistent noncompliance with study requirements, such as failure to return to the study site for scheduled visits.
- Pregnancy and/or breast feeding.
- Documented eGFR_{MDRD} value meeting the criteria defined below:
 - An eGFR value (calculated centrally) that is < 30 mL/min/1.73m²

In all cases, the reason for withdrawal and the date of withdrawal must be recorded in the electronic case report form (eCRF) and in the subject's medical records.

* “Legally authorized representative” means an individual or judicial or other body authorized under applicable law to consent on behalf of a prospective subject to the subject's participation in the procedure(s) involved in the research.

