8.2.2. Stopping Criteria

Subjects must discontinue study medication and be withdrawn from the study if they meet any of the following stopping criteria:

- 30% increase in serum creatinine from Baseline (Visit 1) confirmed by repeat analysis in fully hydrated subject
- 25% decrease from Baseline in cardiac ejection fraction as determined by echocardiogram
- Cerebrovascular event with significant sequelae, including stroke
- An eGFR value of $< 30 \text{ mL/min/1.73m}^2$

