8.3. MISSING DATA

No missing data imputation will be carried out in this study.

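### By-visit eGFR means lose every subject already withdrawn for renal deterioration, so late visits understate decline; the per-patient slope largely does not

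*SAP*

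**What the plan says.** Protocol 8.2.2 makes withdrawal compulsory: "Subjects must discontinue study medication and be withdrawn from the study if they meet any of the following stopping criteria". The renal limits are "30% increase in serum creatinine from Baseline (Visit 1) confirmed by repeat analysis in fully hydrated subject" and an eGFR below 30 mL/min/1.73m2; the cardiac limit is "25% decrease from Baseline in cardiac ejection fraction as determined by echocardiogram". Protocol 11.3.6 repeats them. Protocol 6.4 also lists eGFR below 30, but under permissive wording: "Subjects may discontinue migalastat HCl and withdraw from the study for any reason".

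eGFR and ejection fraction are efficacy endpoints in Protocol 8.3.1 and SAP 17.1. SAP 17.1 has efficacy outcomes "summarized using nominal visits (not including unscheduled visit or early termination) and descriptive statistics". SAP 7.3 leaves unscheduled measurements out of by-visit summaries and uses the first value when a visit is retested. SAP 8.3 adds: "No missing data imputation will be carried out in this study". SAP 6.2 and 17.1 also leave the renal-impairment (Addendum 1.1.2) subject out of the ITT set and the efficacy outcomes.

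SAP 17.1.1 plans a second eGFR summary: a regression slope for each patient over that patient's available visits. SAP 17.1.2 is headed as the same quantity for CKD-EPI.

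**The concern.** The protocol itself expects renal loss: "Since Fabry disease is a chronic condition, typically resulting in declining renal function, and usually requiring life-time treatment". If the subjects who lose most function are withdrawn, and the mean at each later visit is taken over those who remain, then missingness is driven by the quantity being averaged. The error runs one way. Mean change flattens as follow-up lengthens, even when every subject declines at a constant rate.

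The secondary objective is long-term efficacy, and SAP 15 categorises exposure up to 48 months. Late-visit means will therefore be tabulated, and a flat late curve could be read as stable renal function when part of the flatness is selection.

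**Working it through.** **Which values are lost.** A limit crossed at a scheduled visit is a nominal-visit value. Under SAP 7.3 and 17.1 it stays in that visit's table, even if a same-visit retest follows. The subject is missing from the next visit onward. A crossing found only at an unscheduled visit never enters a by-visit table.

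**What the creatinine limit means on the eGFR scale.** The SAP's CKD-EPI equation has exponent -1.209 for creatinine above k. So 1.3^-1.209 = 0.728, a 27% fall in eGFR. A subject with a confirmed fall of that size leaves all later means.

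**Size.** The plan states no expected change, slope or variance, so there is no figure to reproduce. An illustrative simulation used:

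- From the documents: the two renal limits, the 6-monthly visits, and the 48-month horizon.
- Assumed: baseline eGFR mean 70 or 90 (SD 25, values below 30 removed), linear slopes with mean -1, -2 or -3 per year, between-subject slope SD 2 or 4, measurement error 6%, and 200,000 subjects per scenario.

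For each visit, *full* is the mean change if nobody were withdrawn. *Remaining* is the mean over subjects not stopped before that visit, with the crossing visit counted. The understatement is (remaining - full) / |full|.

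48 months:

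| Slope | SD | Baseline mean | Full | Remaining | Gap | Understated | Withdrawn before |
|---|---|---|---|---|---|---|---|
| -1 | 2 | 70 | -4.03 | -3.35 | 0.68 | 17% | 5.9% |
| -1 | 2 | 90 | -4.01 | -3.71 | 0.30 | 7% | 2.0% |
| -1 | 4 | 70 | -3.97 | -0.03 | 3.94 | 99% | 15.0% |
| -1 | 4 | 90 | -4.08 | -1.51 | 2.57 | 63% | 8.7% |
| -2 | 2 | 70 | -8.01 | -6.81 | 1.20 | 15% | 10.5% |
| -2 | 2 | 90 | -8.06 | -7.47 | 0.59 | 7% | 4.2% |
| -2 | 4 | 70 | -7.96 | -2.89 | 5.07 | 64% | 20.2% |
| -2 | 4 | 90 | -7.98 | -4.45 | 3.53 | 44% | 12.6% |
| -3 | 2 | 70 | -12.04 | -10.09 | 1.95 | 16% | 17.6% |
| -3 | 2 | 90 | -12.02 | -10.94 | 1.08 | 9% | 8.0% |
| -3 | 4 | 70 | -11.97 | -5.38 | 6.59 | 55% | 27.2% |
| -3 | 4 | 90 | -11.99 | -7.34 | 4.65 | 39% | 17.5% |

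At 24 months the gap is 0.01 to 0.58 mL/min/1.73m2. That is at most about 5% in nine of the twelve scenarios. In the three with baseline mean 70 and slope SD 4 it is 17% (0.34/1.99), 11% (0.43/4.00) and 10% (0.58/6.02).

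A separate run with assumed baseline mean 85 and SD 22, and an assumed MDRD exponent of -1.154, gave 48-month means of:

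- slope -1, SD 3: -4.0 against -2.6
- slope -2, SD 3: -8.0 against -5.8
- slope -2, SD 4: -8.0 against -3.8
- slope -3, SD 4: -12.0 against -6.5

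That is 28% to 53% understated. With slope SD 2 it was about 10%.

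**Per-patient slope.** In the twelve scenarios the mean slope over available visits (subjects with at least three values) stayed within 0.12 per year of the full-data slope. It was, if anything, slightly steeper (for example -3.12 against -3.00).

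**Ejection fraction.** Assumed: baseline 62 (SD 6), error SD 3, slopes -0.5 or -1 point per year with SD 1 or 2, annual echocardiogram. At 4 years the gap is 0.04 to 0.75 points if the 25% is relative, and at most 0.03 if it is absolute. At most 4.5% are withdrawn before that visit.

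**The case against.** The study is descriptive, efficacy is a secondary and exploratory aim, and attrition is not hidden. SAP 10 counts withdrawals for stopping criteria, n appears at each visit, and listings include early-discontinuation data. Clinically significant-result tables include unscheduled and early-termination visits. Most important, eGFR already has a summary that keeps withdrawn subjects, and subgroup results in SAP 8.5 are built on it.

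Most of this stands. It limits the consequence but does not repair the by-visit eGFR tables, because nothing ties the withdrawal counts to the visit means or tells the reader which eGFR summary to trust. A descriptive mean over a shrinking, selected group can still mislead.

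A reader might infer that the later tables contain only subjects inside the limits. The documents do not support that, since a crossing at a scheduled visit is kept: in the simulation 1.1% to 7.1% of subjects in the 4-year eGFR table were at or over a limit. A reader might also extend the finding equally to LVMi and urine protein. No stopping criterion is defined on either, so any effect there is indirect and depends on an unstated correlation with creatinine or ejection fraction.

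Finally, withdrawn subjects do have end-of-study assessments about 30 days after last treatment (Protocol 8), and SAP Appendix 1 lists End of Study as a presented visit. If their values enter that row, part of the missing information is shown, though off treatment. SAP 17.1 excludes early termination, so the plan does not settle this.

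**Conclusion.** The point holds for by-visit eGFR change at late visits. Its direction follows from the documents: withdrawal depends on the outcome, only nominal visits are averaged, nothing is imputed, and the bias is toward less decline. Its size does not follow from them. Under the assumptions above it is roughly 10% at 48 months with slope SD 2 and about 50% with SD 4. The spread is wide (7% to 99%), and the largest percentage arises where the true mean decline is smallest. At 24 months it is minor in most settings.

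The documents do not support saying that the plan's long-term renal conclusion as a whole is biased, because the slope largely escapes. Nor do they support giving ejection fraction equal weight. Its tables have no slope counterpart, but the effect is probably small and depends on whether the 25% is relative or absolute, which the protocol does not say. The bias arises only to the extent that subjects are in fact withdrawn, and Protocol 6.4 and 8.2.2 differ on whether that is permitted or required at eGFR below 30.

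**What to change.** In SAP 17.1, keep the by-visit tables and:

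1. For eGFR, and for ejection fraction, add the change to the last on-treatment value for every ITT subject, using unscheduled and early-termination values up to last dose, shown with time on study. In one check (slope -2, SD 3, 48 months) this gave -7.5 where the full mean was -8.0 and the remaining-subject mean -5.8. It recovered 1.7 of the 2.2 gap.
2. At each visit, add the cumulative number withdrawn for a stopping criterion and their last on-treatment change.
3. Footnote that later by-visit means exclude subjects already withdrawn, and that the slope is the eGFR summary to read for long-term decline. Because the footnote leans on the slope, also correct SAP 17.1.1, which names study day as the dependent variable; an annualized change needs eGFR regressed on time.
4. State whether withdrawn subjects' values enter the End of Study row of Appendix 1.

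In the protocol, reconcile 6.4 with 8.2.2 on eGFR below 30, and state how the 25% ejection-fraction fall is measured.

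The SAP cost is wording and a few table rows from data already collected. The downsides are small: the last-value row mixes lengths of follow-up, and the reported change becomes less favourable.

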17.1.1. ANNUALIZED CHANGE IN MDRD eGFR

The MDRD eGFR values at every visit will be provided by the central laboratory.

The annualized change (the slope) in MDRD eGFR will be computed over the available visits of each patient between baseline and End of Study (EOS). A simple linear regression between the observed values and the assessment times (study day of the visits as the dependent variable) will be applied to estimate the annualized change.

The duration between baseline and the last post-baseline visit in years (study days of the visit/365.25 days per year) will be presented along with the annualized rate of change for MDRD eGFR.

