10.3.4.2. Efficacy Analyses

Since no hypothesis testing is planned for this study, all efficacy parameters will be summarized using descriptive statistics for subjects in the ITT population. Summaries of the efficacy variables will be provided for the value at baseline and at each post-baseline time point and the change from baseline at each post-baseline time point.

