8.5. EXAMINATION OF SUBGROUPS

Descriptive analyses of the efficacy endpoints (annualized change in MDRD eGFR and CKD-EPI eGFR) will be performed on the following subgroups:

- Males, 24-hr urine protein < 100 mg/24h
- Males, 24-hr urine protein ≥ 100 , <1000 mg/24h
- Males, 24-hr urine protein ≥ 1000 mg/24h
- Females, 24-hr urine protein < 100 mg/24h
- Females, 24-hr urine protein ≥ 100 , <1000 mg/24h
- Females, 24-hr urine protein ≥ 1000 mg/24h

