9. OUTPUT PRESENTATIONS

Appendix 1 shows conventions for presentation of data in outputs.

The templates provided with this SAP describes the presentations for this study as well as format and content of the summary tables, figures, and listings to be provided by IQVIA Biostatistics.

Document: \\quintiles.net\enterprise\Sites\CAMTL\IntProjects\SasData\Amicus\AT1001\AXA23225A\Biostatistics\Documentation\SAP\DR\Amicus_AT1001-042_SAP_Final_v1.0_20190821.docx

Author: Amicus

Version Number: Final v1.0

Version Date: 21AUG2019

Template No.: CS_TP_BS016 Revision 5

Reference: CS_WI_BS005

Effective Date: 01Apr2018

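### SAP 17.1.1 names study day as the dependent variable in the eGFR slope regression, which reverses the model it needs

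*SAP*

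**What the plan says.** SAP 17.1.1 sets the target quantity: "The annualized change (the slope) in MDRD eGFR will be computed over the available visits of each patient", running from baseline to the End of Study visit. The next sentence gives the model: "A simple linear regression between the observed values and the assessment times (study day of the visits as the dependent variable) will be applied", in order to estimate the annualized change. The section then says that the time from baseline to the last post-baseline visit, in years (study days divided by 365.25), "will be presented along with the annualized rate of change for MDRD eGFR".

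The endpoint is used in SAP 8.5: "Descriptive analyses of the efficacy endpoints (annualized change in MDRD eGFR and CKD-EPI eGFR) will be performed on the following subgroups". The six subgroups cross sex with three bands of 24-hour urine protein.

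The Protocol does not define a slope. Its section 10.3.4.2 says only that "Summaries of the efficacy variables will be provided for the value at baseline and at each post-baseline time point", together with the change from baseline.

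**The concern.** The first and last statements in SAP 17.1.1 call for a rate of change of eGFR per unit of time. In ordinary least squares that means eGFR is the response and time is the regressor. The sentence between them assigns the roles the other way round. *Dependent variable* has one standard meaning in regression, so the sentence cannot be read as a loose description of the intended model.

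The variable roles for the MDRD slope are stated nowhere else in the available text. The SAP is marked Final v1.0, and section 5.3 makes it the basis of the final analyses. A program written to the letter would fill the slope table and its six subgroup summaries with a quantity that is not an annual change in eGFR.

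**Working it through.** The documents give no slope figure to reproduce, so the check compares the two orientations directly.

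**Formulas.** For one patient, let x be time and y be eGFR, with Sxx, Syy and Sxy the centred sums of squares and products.

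- Intended (eGFR on time): b = Sxy/Sxx, in mL/min/1.73m2 per unit of time.
- As written (time on eGFR): c = Sxy/Syy, in units of time per mL/min/1.73m2.
- Product: b × c = Sxy²/(Sxx × Syy) = R². Hence 1/c = b/R², which equals b only when the points lie exactly on a line.

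**Worked example.** The six-monthly spacing comes from SAP 17.1; the eGFR values are assumed. Take eGFR 60, 61, 57, 59, 56 at 0, 0.5, 1, 1.5 and 2 years. The means are 1 year and 58.6.

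- Sxx = 1 + 0.25 + 0 + 0.25 + 1 = 2.5
- Sxy = -1.4 - 1.2 + 0 + 0.2 - 2.6 = -5.0
- Syy = 1.96 + 5.76 + 2.56 + 0.16 + 6.76 = 17.2
- Intended slope: -5.0/2.5 = **-2.00 mL/min/1.73m2 per year**
- Literal slope: -5.0/17.2 = -0.2907 years = **-106.2 days per mL/min/1.73m2**
- R² = 25/(2.5 × 17.2) = 0.581
- Reciprocal of the literal slope: 17.2/(-5.0) = -3.44 per year, which is -2.00/0.581

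With no noise, a loss of 2 per year would give 365.25/(-2) = -182.6 days per unit. The literal slope therefore depends on visit-to-visit scatter as well as on the rate of decline.

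**Range over scatter.** The documents give no within-patient SD, so a range is assumed. With a true loss of 2 per year, normal errors, six-monthly visits and 200,000 simulated patients per setting:

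| Visits | Assumed SD | Median R² | Median reciprocal of literal slope (per year) |
|---|---|---|---|
| 5 | 2 | 0.50 | -4.40 |
| 5 | 4 | 0.26 | -7.92 |
| 5 | 6 | 0.20 | -10.71 |
| 9 | 2 | 0.70 | -2.97 |
| 9 | 4 | 0.37 | -5.74 |
| 9 | 6 | 0.21 | -9.20 |

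The correctly oriented slope averaged -1.98 to -2.00 in all six settings. A separate simulation with true losses of 1 and 3 per year and SDs of 2, 5 and 8 gave the same pattern. The intended slope's median stayed at the true value (-0.96 to -1.01, and -2.98 to -3.04). The median reciprocal ran from -2.88 to -11.59 for a true loss of 1, and from -3.63 to -14.61 for a true loss of 3.

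**The case against.** The strongest reply is that this is a one-word slip which its own section resolves. SAP 17.1.1 three times describes a rate of change in eGFR, and only eGFR regressed on time can produce one. A competent programmer would fit that model. This stands. It is the reason for rating the point minor, but it does not make the sentence correct.

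A second reply is that the inflated annual rates need a step the SAP never asks for: someone would have to fit the reversed model, invert the slope and report the result as a rate. This also stands. Those figures show that the literal output cannot be repaired afterwards. They do not estimate bias in this trial, and they rest on assumed eGFR values and SDs. The mismatch of units carries the point without them.

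A third reply is that the output templates cited in SAP section 9, or the remainder of 17.1.2, may show the right unit. Neither is in the available text, where 17.1.2 stops after the CKD-EPI equation, so this cannot be settled. A correct template would lower the risk of a wrong table but would leave the SAP sentence wrong.

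**Conclusion.** The concern holds, as a minor error of specification. As written, the regression yields days per mL/min/1.73m2 and cannot yield the annualized eGFR change that the same section defines. This follows from the wording and from the identity b × c = R², and needs no assumption about the data. The sizes shown (-106.2 days per unit against -2.00 per year, and reciprocals well beyond the true rate) depend on the assumed values.

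The consequence is limited. SAP 7.5 and Protocol 10.1 rule out formal testing, and the eGFR values and changes from baseline by visit in SAP 17.1 do not use the slope. Only the MDRD slope summary and its subgroups in SAP 8.5 are exposed, plus the CKD-EPI slope if 17.1.2 repeats the wording.

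**What to change.** Replace the regression sentence in SAP 17.1.1 with wording such as: *For each patient, eGFR is the dependent variable and time (study day/365.25) is the independent variable; the annualized change is the fitted slope in mL/min/1.73m2 per year.* This also makes explicit the yearly scaling that the term annualized already implies. Check that 17.1.2 and the table templates use the same roles and unit. The cost is one sentence in the SAP, with no effect on data collection or conduct.
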